#### 10.0 EVALUATION DURING TREATMENT/INTERVENTION

#### **Study Calendar**

Regorafenib taken orally will be administered for 3 weeks on /1 week off. One cycle is 28 days. The evaluations/tests scheduled for Cycles 1 through 3+ may be performed up to 3 days prior to the start of the week designated in the table below if not otherwise specified. After Cycle 12 and beyond, MD visits and labs are required every odd cycles, and labs only during even cycles.

1													
	Pre- Study a	C1 Wk 1	C1 Wk 2	C1 Wk 3	C1 Wk 4	C2 Wk 1	C2 Wk 2	C2 Wk 3	C2 Wk 4	C3+ Wk1	C12+ Even Wk 1	C13+ Odd Wk 1	Off Study g
Regorafenib b		X	X	X	-	Xp	X	X	7	Х	X	X	
Informed consent	X												
Medical history	X												
Concurrent meds	X	X-	ļ									X	X
Physical exam	X	Χď	X	X		X		X		Χ †		X †	X
Vital signs	X	Xq	X	X		X		X		X		X †	X
Blood pressure													
monitoring (on non- clinic weeks) j					Х		Х						
Weight	Х	Χď	Х	Х		Χ		Χ		Χ †		Χ †	X
Performance status	Х	Xq	Х	Х		Х		Χ		Χ †		Χ †	Х
CBC w/diff, plts	Х	Xe		Х		Х		Х		Χ †	X †	Χ †	X
Comprehensive panel c	Х	Xe		Χ		Х		Х		Χ †	X †	Χ †	Х
Lipase, Amlyase blood test	Х												
Coagulation studies l	Х	Х		Х		Х		Х		Χ †	Χ †	Χ †	
ECG	Х												
Beta-HCG (serum)	$X^k$												
Request for archival tumor tissue	Х												
Research tumor biopsy h	Х												
Research blood draw	Х												
Adverse event		X										∨m	Х
evaluation												,,	^
Tumor measurements i	х	CT and/or MRI will be performed every 8 weeks (+/- 1 week) (or approximately every 2 cycles). After 10 months, scans will be performed every 12 weeks (+/- 1 week)(or approximately every 3 cycles). Documentation (radiologic) must be provided for patients removed from study for progressive disease. Objective responses should be confirmed with a second assessment performed at least 4 weeks later. Every effort should be made to have tumor measurements performed 6 months (+/- 1 week) after the start of treatment, if possible, for assessment of the primary endpoint.											
	a: See Section 8.0 for the timing of these tests/evaluations prior to the start of therapy. b: Patients will start the study taking regorafenib 120 mg orally daily for 3 weeks in a 4 week cycle. Patients for whom regorafenib dose reduction was not performed or required may have their treatment dose increased to the FDA-approved dose of 160 mg daily orally for 3 weeks in a 4-week cycle in cycle #2 or beyond (this is not mandatory). If a patient misses a dose of regorafenib for personal reasons (i.e. forgetting to take medication, nausea, etc.), the missed dose should be documented on the patient's pill diary (Appendix B). Missed doses not directed by the investigator(s) that constitute ≤ 20% of the mandated doses for a given cycle will not be considered (a) protocol violation(s). Doses held at the discretion of the physician are never protocol violations. Missed or skipped doses will not be made up (i.e., the week/day count on therapy will continue regardless of whether doses												

IRB#: 13-244 A(9)

have been missed or skipped).

- c: Albumin, alkaline phosphatase, total bilirubin, bicarbonate, BUN, calcium, chloride, creatinine, glucose, LDH, phosphorus, potassium, total protein, SGOT [AST], SGPT [ALT], sodium.
- d: These Week 1 evaluations may be performed up to 3 days prior to the start of treatment.
- e: These Week 1 laboratory tests may be done up to 7 days prior to starting treatment. It is unnecessary to repeat these laboratory tests if the screening assessments of the same tests were performed within 7 days prior to the first dose of therapy.
- f: After the completion of Cycle 2, the CBC, serum chemistry blood tests, coagulation studies (if required), physical examinations, vitals signs, performance status, and weight will be done once every cycle, preferably on week 1 of every cycle. If the patient cannot be seen on week 1, these evaluations may be completed up to 1 week prior or during another week within the cycle at the discretion of the treating physician.
- g: Off-study evaluation will be performed within 30 days of the patient's last dose of regorafenib.
- h: Patients may be exempt from biopsy if either the investigator or person performing the biopsy judges that no tumor is accessible for biopsy or that biopsy poses too great of a risk to the patient. Patients may also be exempt if frozen tumor tissue has been collected within 12 months of study enrollment that the Principal Investigator deems is appropriate/sufficient for analysis on this protocol. For those undergoing research biopsy on protocol, radiologic guidance (CT, MRI or ultrasound guided) approaches and obtaining multiple cores to ensure sufficient biopsy material (at least 3 cores preferred) are allowed as long as it is considered reasonably safe for the patient. Tissue will be flash frozen in liquid nitrogen as directed by the Principal Investigator (the biopsy sample(s) will be placed into a cryovial, which will be submerged in a liquid nitrogen bath until the tissue is frozen.) Some tissue may be prepared by fixation according to institutional guidelines if directed by the Principal Investigator.
- i: The treating physician may reschedule radiology scans due to treatment delays at his or her discretion. If the patient has CT and/or MRI scans completed early for any reason (i.e. suspicion of disease progression), the next set of scans may be ordered in 8 weeks (+/- 1 week) from that assessment (or in 12 weeks (+/- 1 week) for patients who are on treatment for more than 10 months). Every effort should be made to have tumor measurements performed 6 months (+/- 1 week) after the start of treatment, if possible, for assessment of the primary endpoint.
- The onset of regorafenib-induced hypertension often occurs during the first cycle of treatment for most patients who develop hypertension. During the first 6 weeks of treatment, it is strongly recommended that patients have their blood pressures checked even in weeks that they are not evaluated at MSKCC. There are no restrictions on how the blood pressure is to be obtained during those weeks, and can include monitoring on home blood pressure equipment, at other physician offices, at MSKCC, or at commercial outlets. Blood pressure values may be recorded in the pill diaries that will be reviewed at each MSKCC clinic visit or or verbally reported to the study team. If the systolic blood pressure is >150 mm Hg and/or the diastolic blood pressure is >90 mm Hg and/or symptoms develop that are perceived to be related to elevated blood pressure (for example headaches or visual disturbance), patients will be instructed by study staff to contact their study physician immediately for guidance. A re-check of the blood pressure can be requested at the study physician's discretion to determine the accurate value of the patient's blood pressure before protocol-dictated action(s) is/are taken in response to a reported blood pressure value (this applies both to recommended and protocolmandated blood pressures taken at MSKCC or outside of MSKCC). The study physician may at his/her discretion determine which external values likely reflect the true blood pressure to guide clinical decision-making.
- k. Serum pregnancy test is required within 14 days of drug treatment for all women of child-bearing potential.
- I. Coagulation studies consist of the prothrombin time (PT), partial thromboplastin time (PTT), and international normalized ratio (INR). These are only required as indicated on the calendar for patients on anti-coagulation medications (heparin, low-molecular weight heparin, or coumadin). These do not need to be checked for patients not on these anti-coagulation medications.
- m. During even cycles after cycle 12, adverse event will be conducted by phone assessment.

IRB#: 13-244 A(9)

#### 11.0 TOXICITIES/SIDE EFFECTS

The starting dose of regorafenib is 120 mg once daily. Study medication will be administered on a 3 weeks on/1 week off schedule (3 weeks out of every 4). Patients for whom regorafenib dose reduction was not performed or required may have their treatment dose increased to the FDA-approved dose of 160 mg daily orally for 3 weeks in a 4-week cycle in cycle #2 or beyond (this is not mandatory).

Doses will be delayed or reduced for clinically significant hematologic and non-hematologic toxicities that are related to protocol therapy according to the guidelines described in sections below. Dose modifications will follow predefined dose levels. Dose adjustments for hematologic toxicity are based on the blood counts obtained in preparation for the day of treatment.\

For patients who must undergo a procedure or surgery while on study that requires wound healing or involves risk for significant bleeding, regorafenib should be held 2 weeks prior to the scheduled surgery/procedure. The decision to resume reografenib after the surgery/procedure should be based on clinical judgement of adequate wound healing

#### 11.1 General Considerations for Managing Regorafenib-related Adverse Events

This section contains general recommendations for the management of adverse events. Patients developing a regorafenib-related CTCAE Grade 1 or 2 adverse events may have their dose continued at the same dose level.

Notes: The recommendations for the management of adverse events in this section are to serve as general guidelines; dose reductions or delays for any event of any CTCAE grade may always be considered for safety reasons at the discretion of the treating investigator. If a subject experiences more than one toxicity, dose reduction should be according to the toxicity with the highest grade. In the case of two or more toxicities of the same grade, the investigator may dose reduce according to that deemed most causally related to study treatment.

The modifications of regorafenib will follow the following predefined dose levels:						
Dose level +1 (standard starting dose) 160 mg po qd Four 40-mg tablets of regorafenib						
Dose level 0	120 mg po qd Three 40-mg tablets of regorafenib					
Dose level - 1	80 mg po qd	Two 40-mg tablets of regorafenib				

(RB PB

IRB#: 13-244 A(9)

	Recommended dose modification for toxicities except hand-foot-skin reaction, hypertension, and ALT/AST/bilirubin for adverse events related to regorafenib						
NCI-CTCAE v4.0 a	Dose Interruption b	Dose Modification b	Dose for Subsequent Cycles				
Grade 0-2	Treat on time	No change	No change				
Grade 3	Delay until ≤ Grade 2°	Reduce by 1 dose level	If dose was reduced and toxicity remains < Grade 2, dose re-escalation can be considered at the discretion of the treating investigator. If dose is re-escalated and toxicity (≥ Grade 3) recurs, institute permanent dose reduction.				
Grade 4	Delay until ≤ Grade 2°	Reduce by 1 dose level. Permanent discontinuation can be considered at treating investigator's discretion.					

a. NCI-CTCAE = National Cancer Institute - Common Terminology Criteria for Adverse Events, version 4.0

(RB PB

b. Dose modification or interruption is not required for alopecia, non-refractory hypersensitivity and asymptomatic laboratory abnormalities. Dose modification or interruption is not required for nausea, vomiting and diarrhea if optimal supportive management has not been instituted.

c. If no recovery after a 4 week delay, treatment should be permanently discontinued unless subject is deriving clinical benefit.

IRB#: 13-244 A(9)

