#### 13.0 CRITERIA FOR REMOVAL FROM STUDY

- Disease progression on treatment with regorafenib
- Patients may be removed from the study for protocol non-compliance.
- If at any time the patient develops unacceptable toxicity he/she will be removed from study.
- Participants can be removed from the study at any time if the study doctor feels that it is in their best interest to do so.
- Patients may withdraw consent from the study at any time.

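### The Section 11.1 exemption for symptom-free laboratory findings has no grade limit, so an asymptomatic Grade 3-4 neutropenia or thrombocytopenia escapes the recommended hold and dose reduction

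*Combined protocol and SAP*

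**What the plan says.** Section 11.0 starts patients at 120 mg daily, three weeks on and one week off. It provides that treatment is held back or lowered in the case of "clinically significant hematologic and non-hematologic toxicities that are related to protocol therapy according to the guidelines described in sections below". The next relevant sentence reads: "Dose adjustments for hematologic toxicity are based on the blood counts obtained in preparation for the day of treatment". Neither sentence gives a neutrophil or platelet threshold, and clinical significance is not defined. The same section sets the escalation condition: "Patients for whom regorafenib dose reduction was not performed or required may have their treatment dose increased to the FDA-approved dose of 160 mg". This is open from cycle 2 and is not mandatory.

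The table in Section 11.1 covers all regorafenib-related toxicities except "hand-foot-skin reaction, hypertension, and ALT/AST/bilirubin for adverse events related to regorafenib". For Grade 3 it recommends waiting until Grade 2 or better and then going down one dose level. For Grade 4 it recommends the same, with permanent discontinuation as an option. Footnote b is marked on both the interruption and the modification column headings: "Dose modification or interruption is not required for alopecia, non-refractory hypersensitivity and asymptomatic laboratory abnormalities".

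Three statements leave room for judgment. Section 11.1 says "The recommendations for the management of adverse events in this section are to serve as general guidelines" and adds that "dose reductions or delays for any event of any CTCAE grade may always be considered for safety reasons". Section 13.0 says: "If at any time the patient develops unacceptable toxicity he/she will be removed from study".

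**The concern.** A low neutrophil or platelet count is first of all a laboratory finding. It can turn up on a scheduled blood count before there is any fever or bleeding, and at that point it is by definition symptom-free. A severe count of that kind is one for which a hold-and-reduce rule is useful, yet the footnote's wording takes it out of that rule.

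Other parts of the protocol suggest that this was not intended. Section 11.0 bases hematologic adjustments on counts, not symptoms. Section 9.2 does not let growth factors stand in for a required dose reduction, which presupposes that some hematologic reductions are required. Section 11.4 manages liver tests by grade with no symptom condition.

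The stake is patient safety and consistent handling. Two investigators facing the same Grade 3 platelet count could act differently, and each could cite the protocol. The one who did nothing could also raise the dose in the next cycle without departing from the text.

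**Working it through.** The protocol gives no figure for this point, so there is nothing to reproduce. The check sets the sections side by side and then sizes the dose difference.

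**Step 1: which guideline covers these counts.** Section 11.2 covers hand-foot skin reaction, 11.3 hypertension, and 11.4 ALT, AST and bilirubin. Neutropenia and thrombocytopenia appear in none of them. They fall only under the 11.1 table.

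**Step 2: whether footnote b reaches Grade 3-4 counts.** The table already calls for no change at Grades 0 to 2. The footnote therefore has an effect only at Grades 3 and 4, and it cannot be read as dealing with mild changes alone. It names no laboratory test as an exception.

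**Step 3: whether Section 11.0 restores the rule.** Its delay-or-reduce sentence works through the guidelines that follow, which leads back to the table and its footnote. Its count sentence says which data to use. It does not say at what count to act or what to do. Neither sentence brings back a hold or reduction for a symptom-free severe count.

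**Step 4: escalation.** The condition is that no reduction was made or required. If footnote b means that none is required and the investigator makes none, the condition is met. The Section 10.0 calendar has a blood count in week 3 of cycle 1, so a severe count can be known before a cycle 2 escalation.

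**Step 5: size.** Inputs: 21 dosing days per 28-day cycle (Section 9.1), and dose levels of 80, 120 and 160 mg (Section 11.1). Dose per cycle = 21 × daily dose.

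- 80 mg: 21 × 80 = 1,680 mg
- 120 mg: 21 × 120 = 2,520 mg
- 160 mg: 21 × 160 = 3,360 mg

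For a patient at 120 mg, the comparator while the one-level reduction is in force is 1,680 mg:

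- investigator holds and reduces anyway: 1,680 / 1,680 = 1.0
- dosing continues unchanged: 2,520 / 1,680 = 1.5
- dose is then escalated: 3,360 / 1,680 = 2.0

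For a patient already at 160 mg who continues unchanged: 3,360 / 2,520 = 1.33.

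The Grade 3 row also allows later re-escalation at the investigator's discretion. Once a patient reduced to 80 mg is back at 120 mg, the comparator becomes 2,520 mg. The ratios then fall to 2,520 / 2,520 = 1.0 and 3,360 / 2,520 = 1.33.

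**Step 6: frequency.** The documents give no cytopenia rate for regorafenib. The most frequent Grade 3 or higher events that Section 3.0 lists from the phase III colorectal cancer trial and the phase III GIST trial include no cytopenia.

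**The case against.** The strongest reply is that a fair reader would let the specific sentence govern the general one. The count sentence in Section 11.0 is about hematology and looks to counts, while footnote b speaks of laboratory findings at large. The growth-factor rule in Section 9.2 points the same way. In addition, the Grade 3 and Grade 4 rows are themselves headed as recommendations, so the footnote removes a recommendation and not a mandate. It does not tell anyone to continue dosing.

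Much of this stands. The intent was probably to act on counts, and an investigator is free to do so at any grade. But the count sentence supplies neither a threshold nor an action, so letting it govern still leaves the reader with no instruction for a symptom-free severe count. The discretion clause permits a hold or reduction without recommending one, and removal for unacceptable toxicity depends on a term that is not defined.

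A reader might also infer a monitoring gap for patients on anticoagulants, because the extra tests scheduled for them are PT, PTT and INR. The documents do not support that. Blood counts with platelets are on the Section 10.0 calendar for every patient: weeks 1 and 3 of cycles 1 and 2, then once per cycle. The gap is in what to do with the result, not in obtaining it.

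**Conclusion.** The point holds as an over-broad exemption. Taken at its word, footnote b leaves an asymptomatic regorafenib-related Grade 3-4 neutropenia or thrombocytopenia without a recommended hold or reduction. If no reduction is made, optional escalation to 160 mg stays open.

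The per-cycle dose difference from 120 mg is 1.5-fold if dosing continues. It is 2.0-fold only if the investigator takes no action on the count and also chooses the escalation. Both figures hold only while the reduction would have been in force, and they measure dose, not risk. Frequency is unknown and probably low.

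Some stronger readings are tempting but not supported:

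- **A contradiction between Sections 11.0 and 11.1.** Section 11.0 defers to the later sections, so the two can be read together.
- **Sustained double dosing.** The table's own re-escalation provision shrinks the gap, and 160 mg is the dose that the protocol describes as FDA-approved.
- **Unmanaged liver toxicity.** ALT, AST and bilirubin are outside this table and follow Section 11.4.
- **Damage to the trial's conclusions.** No primary or secondary endpoint is affected.

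This is a cheap improvement to a safety rule.

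**What to change.** In footnote b, directly after the words on symptom-free laboratory findings, add: *other than Grade 3-4 neutropenia or thrombocytopenia, which follow the Grade 3 and Grade 4 rows whether or not symptoms are present*. Other laboratory changes without symptoms stay exempt as now.

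The clause brings these counts under the reduction rows and so within the existing escalation condition: a patient reduced under those rows no longer qualifies for the rise to 160 mg on that condition. A separate permanent bar, written into each of the five places where the escalation sentence appears (Sections 4.2, 9.1, 9.3.3, calendar footnote b, 11.0), is not needed. It would also block patients whose count had fully recovered, although the table allows discretionary re-escalation after a Grade 3 event.

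The cost is one clause. The blood counts are already scheduled, so no tests, data or patients are added. The downside is that a few patients with symptom-free severe counts would be held or reduced who might otherwise have continued. Investigators keep their discretion, because the rows remain general guidelines.

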#### 11.2 Hand-foot skin reaction related to regorafenib

Grading for Hand-Foot-Skin-Reaction							
	Grade 1	Grade 2	Grade 3				
NCI-CTCAE v4.0 Palmar-plantar erythrodysesthesia syndrome a	Minimal skin changes or dermatitis (e.g., erythema, edema, or hyperkeratosis) without pain	Skin changes (e.g., peeling, blisters bleeding, edema, or hyperkeratosis) with pain	Severe skin changes (e.g., peeling, blisters, bleeding, edema, or hyperkeratosis) with pain				
Further description/ examples of skin changes	Numbness, dysesthesia / paresthesia tingling, painless swelling, or erythema of the hands and/or feet	Painful erythema and swelling of the hands and/or feet	Moist desquamation, ulceration, blistering, or severe pain of the hands and/or feet				
Effect on activities	Does not disrupt normal activities	Limiting instrumental activities of daily life (e.g., preparing meals, shopping for groceries or clothes, using the telephone, managing money)	Limiting self-care activities of daily life (e.g., bathing, dressing and undressing, feeding self, using the toilet, taking medications) and not bedridden				
a Palmer-nlanter eryth	rodysesthesia syndrome is a	a disorder characterized	hy redness marked				

a. Palmer-planter erythrodysesthesia syndrome is a disorder characterized by redness, marked discomfort, swelling, and tingling in the palms of hands or the soles of the feet.

At first occurrence of HFSR, independent of grade, prompt institution of supportive measures such as topical emollients, low potency steroids, or urea-containing creams should be considered.

Recommended (not mandated) prevention/management strategies for skin toxicities consistent with HFSR are summarized below:

#### Control of calluses

Before initiating treatment with regorafenib:

- · Check condition of hands and feet.
- Suggest a manicure/pedicure, when indicated.
- Recommend pumice stone use for callus or 'rough spot' removal.

#### During regorafenib treatment:

- Avoid pressure points.
- Avoid items that rub, pinch or create friction.

- a. More conservative management is allowed if judged medically appropriate by the investigator.
- b. If toxicity returns to Grade 0-1 after dose reduction, dose re-escalation is permitted at the discretion of the investigator if subject has completed one cycle at reduced dose without recurrence of event.
- c. If there is no recovery after a 4-week delay, treatment with regorafenib will be discontinued permanently.
- d. Subjects requiring > 2 dose reductions should go off protocol therapy.
- e. The maximum daily dose is 160 mg.

#### 11.3 Hypertension related to regorafenib

Hypertension is a known AE associated with regorafenib treatment. The management of hypertension, including the choice of antihypertensive medication, will be performed according to local standards and to the usual practice of the investigator. Every effort should be made to control blood pressure by medical means other than study drug dose modification.

IRB#: 13-244 A(9)

Antihypertensive Therapy	Regorafenib Dosing
None	
 
Continue regorafenib
 
Consider increasing blood pressure (BP) monitoring
 

 
Treat with the aim to achieve diastolic BP ≤ 90 mm Hg:
 
If BP previously within normal limits, start anti-hypertensive monotherapy
 
If patient already on anti-hypertensive medication, titrate up the dose.
 
	Continue regorafenib     If symptomatic, hold regorafenib until symptoms resolve AND diastolic BP ≤ 90 mm Hg a . When regorafenib is restarted, continue at the same dose level.
Treat with the aim to achieve diastolic BP ≤ 90 mm Hg: Start anti-hypertensive medication  AND/OR Increase current anti-hypertensive medication  AND/OR AND/OR Add additional anti-hypertensive medications.	
 
Hold regorafenib until diastolic BP ≤ 90 mm Hg, and if symptomatic, until symptoms resolve.a
 
When regorafenib is restarted, continue at the same dose level.
 
If BP is not controlled with the addition of new or more intensive therapy, reduce by 1 dose level.b
 
If Grade 3 hypertension recurs despite dose reduction and antihypertensive therapy, reduce another dose level.c
 

Per institutional guidelines	Discontinue therapy
	None  • Treat with the aim to achieve diastolic BP ≤ 90 mm Hg: • If BP previously within normal limits, start anti-hypertensive monotherapy • If patient already on anti-hypertensive medication, titrate up the dose.  Treat with the aim to achieve diastolic BP ≤ 90 mm Hg: Start anti-hypertensive medication  AND/OR Increase current anti-hypertensive medication  AND/OR AND/OR Add additional anti-hypertensive medications.

- a. Patients requiring a delay of >4 weeks should go off protocol therapy
- b. If BP remains controlled for at least one cycle, dose re-escalation permitted per investigator's discretion.
- c. Patients requiring >2 dose reductions should go off protocol therapy.

IRB#: 13-244 A(9)

